1.2.2. Pembrolizumab

Pembrolizumab is an immune stimulatory anti-PD1 antibody with high levels of activity in multiple tumour types, licensed for the treatment of metastatic melanoma and non-small cell lung cancer. Formerly known as lambrolizumab and MK-3475, pembrolizumab is a potent and highly selective humanised monoclonal antibody (mAb) of the IgG4/kappa isotype designed to directly block the interaction between PD-1 and its ligands, PD-L1 and PD-L2. The variable region sequences a very-high-affinity mouse antihuman PD-1 antibody (dissociation constant, 28 pM) and is grafted into a human IgG4 immunoglobulin with a stabilising S228P Fc alteration. The IgG4 immunoglobulin subtype does not engage Fc receptors or activate complement, thus avoiding cytotoxic effects of the antibody when it binds to the T cells that it is intended to activate[20].

Immunotherapy trials to date have shown results that improve survival but also have a prolonged duration of response leading to improved overall survival [8, 21-24]. In the first in-human phase I dose escalation study of pembrolizumab in solid tumours (KEYNOTE-001), the 1 year overall survival rate in 411 melanoma patients was 71%[25]. Long-term efficacy data of 655 patients showed the overall response rate (ORR) was 34%, with 6% complete response rate and the duration of response ranged from 6 to 98 weeks. With the continuing emerging data of improved ORR and a prolonged duration of response in melanoma patients, NICE approved pembrolizumab in October 2015, for the treatment of patients with unresectable or metastatic melanoma and disease progression following ipilumumab and, if BRAF V600 mutation positive, previous failed treatment with a BRAF inhibitor (vemurafenib and dabrafenib) or MEK inhibitor (trametinib).

1.2.3. Pembrolizumab known benefits and risks

Pembrolizumab is generally well tolerated over a spectrum of tumour types and demonstrates a favourable safety profile in comparison to chemotherapy. Safety data from over 2700 patients has reported the most common adverse events of all grades were diarrhoea, cough, pruritis, arthralgia, rash, pyrexia and back pain (Pembrolizumab Investigator Brochure, Merck, Sharp & Dohme). Common grade 3-4 drug related adverse events were anaemia, raised alanine aminotransferase and aspartate aminotransferase.

Immune toxicities are well known among the immunotherapy drugs. Immune-mediated adverse reactions of all grades included hypothyroidism (8.4%), hyperthyroidism (3.4%), pneumonitis (3.4%), colitis (1.8%), severe skin reactions (1.4%), hepatitis (0.7%), hypophysitis (0.6%), diabetes mellitus (0.2%) and nephritis (0.1%). Other immune-mediated adverse reactions of clinical significance were reported in less than 1% of patients included uveitis, myositis, Guillian-Barre syndrome and pancreatitis. Events have been reported to occur from as early as the first dose to several months after the last dose of treatment and early recognition can allow initiation of symptomatic treatment preventing delays and discontinuation of treatment. Complications requiring steroids or immunosuppression are commonly reversible.

The first trial to report clinical activity of an immune check point inhibitor in TNBC was a phase 1b trial (KEYNOTE-012) showing that single agent pembrolizumab given at 10mg/kg IV once every 2 weeks (Q2W) was well tolerated and effective[26]. Twenty-seven heavily pre-treated recurrent or metastatic TNBC positive for PD-L1 were treated showing 18.5% of evaluable patients responded with one complete response, 4 partial

responses and 7 stable disease responses. Patients with a LDH greater than twice the upper limit of normal, which represents rapidly progressive disease had no response to pembrolizumab. Three patients remained on pembrolizumab for at least 11 months, which supports previous suggestions of the durability of pembrolizumab. Previous studies have mentioned the use of PD-L1 as a biomarker for response. However this study lacked correlation between the degree of PD-L1 positivity and response, questioning the use of PD-L1 as an appropriate biomarker [26].

In KEYNOTE-012, the main toxicities of any grade included arthralgia (18.8%), fatigue (18.8%), myalgia (18.8%) and nausea (15.6%). There were five grade 3 treatment related adverse events: anaemia, aseptic meningitis (successfully treated with pembrolizumab interruption and steroids for 6 weeks, with reintroduction of pembrolizumab at a reduced dose), lymphopenia, headache and pyrexia. The patient who had aseptic meningitis had a prolonged partial response and remained on treatment for more than 17 months. There was one treatment related death due to disseminated intravascular coagulation in a patient who had with rapidly progressive disease having had three previous lines of treatment. There were a total of three immune related toxicities; grade 3 colitis (reported 40 days after the last pembrolizumab dose and after starting capecitabine), grade 3 hepatitis and grade 2 hypothyroidism[26]. Pembrolizumab may be given safely in combination with radiotherapy with no apparent increase in adverse effects [27-29]. Pembrolizumab has been given concurrently with adjuvant radiotherapy in completed and ongoing phase III trials (NCT03725059, NCT03036488).

1.2.4. Rationale for pembrolizumab dose selection/regimen

A fixed dose regimen will simplify the dosing regimen to be more convenient for physicians and to reduce potential for dosing errors. It will reduce complexity in the logistical chain at treatment facilities and reduce wastage. A population pharmacokinetic (PK) model, which characterised the influence of body weight and other patient covariates on exposure, has been developed. The PK profile of pembrolizumab is consistent with that of other humanised monoclonal antibodies, which typically have a low clearance and a limited volume of distribution. Since the anti-tumor effect of pembrolizumab is driven through reactivation of adaptive immune response by blocking PD-1 expressed on T-cells, but not direct binding to cancer cells, once the PD-1 on T-cells are fully saturated by pembrolizumab, the shape of the exposure-response relationship among indications is expected to be similar. This is supported by exposure-response analysis in multiple indications. A flat exposure response relationship was demonstrated between pembrolizumab exposure (or dose) and efficacy or safety within the dose range of 2 to 10 mg/kg or 200 mg to 10 mg/kg (exposure at 2 mg/kg Q3W is similar to exposure at 200 mg Q3W). The similarity in efficacy between the tested dose regimens is further supported by comparisons of overall response rate (ORR)/survival outcomes for the tested dose regimens in the melanoma and NSCLC indications. A fixed dose regimen of pembrolizumab is now standard in ongoing pembrolizumab trials. A fixed dose of pembrolizumab 200mg every 3 weeks has been selected for the c-TRAK TN trial.

1.2.5. Blinding in the c-TRAK TN trial (prior to protocol v6.0)

Prior to the implementation of protocol v6.0 during the randomised component of the trial, ctDNA analysis and randomisation were performed independently of the recruiting site in order to keep the treating team and patient blinded to the ctDNA result. The ctDNA analysis was performed centrally by the c-TRAK TN central laboratory. Randomisation to the pembrolizumab treatment/observation groups was performed centrally by the ICR-CTSU, triggered by notification from the central laboratory of a positive ctDNA result. If the patient was allocated to the pembrolizumab treatment group, the Principal Investigator (or designated investigator) was notified by the ICR-CTSU, in order to confirm continued patient consent and perform eligibility checks to start pembrolizumab treatment. Such patients (and their treating team) were therefore 'unblinded' to a positive ctDNA result. If the patient is allocated to the observation group, the treating team and patient were not informed that randomisation had taken place, in order to maintain the blind to a positive ctDNA result and the patient would continue with blinded ctDNA surveillance for up to two years from start of ctDNA surveillance. By keeping both the treating team and patient blind to ctDNA test results the study aimed to avoid unnecessary anxiety in otherwise asymptomatic patients and avoid pressures to restart treatment. Given the uncertainty of the clinical implication of a positive ctDNA result at the time of trial initiation, knowledge of such may have caused concern if no treatment was offered and bias would be introduced if such patients and investigators were blinded to the results of CA125 measurements done every 3 months during routine follow-up, showed no evidence of a survival benefit with early treatment of relapse on the basis of a raised CA125 concentration alone[30]. This supported the need for blinding of ctDNA surveillance results in the c-TRAK trial.

Following the implementation of protocol v6.0 whereby patients transfer to the non-randomised component of the trial, all ctDNA results will be open, and all ctDNA positive patients will be allocated to pembrolizumab intervention.

1.3. Description of Population

Patients with moderate or high risk early stage triple negative breast cancer who have completed neoadjuvant chemotherapy and surgery, or have completed primary surgery and are due to receive/are receiving adjuvant chemotherapy, will be invited to participate. Where radiotherapy is indicated, patients will be eligible for trial entry before/during radiotherapy. All patient groups should ideally be registered as early as possible in their treatment pathway to allow more time for tissue screening to be completed.

2. TRIAL OBJECTIVES

2.1. Primary Objectives

- To assess whether digital PCR ctDNA assays, as a non-invasive biomarker on serial blood samples, can predict which patients are at highest risk of relapse and identify patients with minimal residual disease not visible on imaging.
- To assess whether pembrolizumab results in a sustained clearance of ctDNA in patients who have completed treatment for moderate or high risk early stage triple negative breast cancer, but have minimal residual disease (MRD) detected by serially assessed ctDNA analysis.

2.2. Secondary Objectives

- To assess time to first positive ctDNA detection from entry into the ctDNA surveillance.
- To assess the rate of detection of overt metastatic disease at the time of first ctDNA detection.
- To assess the median lead-time between ctDNA detection and relapse in the pembrolizumab treatment and observation groups.
- To assess sustained clearance of ctDNA in the observation group.
- Safety and tolerability of pembrolizumab.
- To assess the proportion of patients allocated to receive pembrolizumab who start pembrolizumab.

NB. Secondary objectives relating to the observation group will be evaluated in the patients randomised to the observation group prior to the implementation of protocol v6.0.

2.3. Exploratory Objectives

- To explore differences in time between ctDNA detection and disease relapse, and disease free survival, between patients in the pembrolizumab and the observation groups.
- To explore predictors of sustained ctDNA clearance on pembrolizumab.
- To explore potential predictors of relapse and ctDNA detection, and alternative definitions of ctDNA clearance.
- To assess the association between ctDNA clearance and time to recurrence in the pembrolizumab group.

NB. Exploratory objectives relating to the observation group will be evaluated in the patients randomised to the observation group prior to the implementation of protocol v6.0.

3. TRIAL DESIGN

c-TRAK TN is a multi-centre, single-arm, phase II trial that uses ctDNA surveillance to direct intervention, in patients with moderate or high-risk early stage triple negative breast cancer, with no evidence of distant metastatic disease, who have completed standard therapy (surgery and neoadjuvant/adjuvant chemotherapy). Eligible patients may be enrolled straight after surgery or before/during adjuvant chemotherapy, or before/ during adjuvant radiotherapy, if indicated.

The trial consists of tissue screening, ctDNA surveillance and a therapeutic trial. If suitability is confirmed following tissue screening, patients will undergo serial ctDNA surveillance, with allocation to treatment with

pembrolizumab in the therapeutic trial triggered by the detection of minimal residual disease (indicated by a ctDNA positive result) on or before their 12 month ctDNA surveillance assessment.

Prior to the implementation of protocol v6.0 during the randomised component of the trial, ctDNA surveillance was blinded and the detection of minimal residual disease (indicated by a ctDNA positive result) on or before the 12 month ctDNA surveillance assessment triggered randomisation to treatment with pembrolizumab or observation (on a 2:1 ratio).

Following the implementation of protocol v6.0, patients will be asked to transfer to the non-randomised component of the trial, all patients who were previously randomised to observation and remain in ctDNA surveillance will transition to the non-randomised component of the trial following re-consent, and be allocated to pembrolizumab at the next positive ctDNA result.

On 19th March 2020, conditions were put in place to temporarily suspend ctDNA surveillance due to the COVID-19 outbreak. When trial activities are able to resume, the 12 month active surveillance period may be extended by a proportional amount of time to counteract the loss of surveillance samples for each patient during the suspension. For example, if ctDNA surveillance is halted for a duration of time which means that a patient misses **one** ctDNA surveillance sample, active surveillance will be extended beyond the original 12 months to include **one** of the designated exploratory samples (planned to be collected between months 12 and 24). Patients who are ctDNA positive in this extended period will be assessed in the protocol as if they were within in the originally planned 12 month window, and allocated to treatment.

3.1. Tissue Screening and ctDNA Surveillance

Entry into the tissue screening part of the trial will require mandatory provision of tissue from two archival tumour samples and provision of blood samples for germline DNA analysis and additional ctDNA analysis. For patients who have had tumours previously sequenced outside of the c-TRAK TN trial (for example, but not limited to, in the Genomics England Limited 100,000 genome initiative (GEL)), the time required for tissue screening may be significantly reduced if the report confirming the results of the tumour sequencing and the mutation(s) detected can be provided to the c-TRAK TN central laboratory. Patients will be asked to permit access to the report at the time of consent for trial entry. Please refer to section 7.1.2 for further details of the trial requirements for patients with prior sequencing information available.

The tissue and blood samples will be sent to the c-TRAK TN central laboratory for mutation analysis. If trackable mutations are detected in the patient's tumour tissue, ctDNA assays will be personalised and developed for the mutations found in each individual patient's cancer, and the ICR-CTSU will inform the treating team that ctDNA surveillance can be initiated.

If no mutations can be detected in the patient's tumour tissue, or if it is not possible to develop a ctDNA assay, this will be considered a screen failure, and the ICR-CTSU will inform the treating team that ctDNA surveillance should **not** be initiated. Patients with a mutation analysis screen failure will not be entered into ctDNA surveillance and will not be followed up within the c-TRAK TN trial.

Multifocal tumours where tissue screening reveals multiple mutations can be included **where deemed eligible by the Chief Investigator** or, if unavailable, the designated TMG member. This will be assessed on a case by case basis and the ICR-CTSU will inform the treating team whether or not ctDNA surveillance can be initiated.

Patients with tumour tissue in which mutations are detected and for which a ctDNA assay can be developed should start ctDNA surveillance once they have completed standard treatment, including adjuvant chemotherapy, except when receiving adjuvant capecitabine. If receiving capecitabine, patients should

commence ctDNA surveillance 3 months (+/- 2 weeks) after starting capecitabine and treatment can continue while ctDNA surveillance is ongoing. Patients who have stopped capecitabine prior to completing 3 months of treatment for any reason other than disease recurrence are also permitted to start ctDNA surveillance. Patients may start ctDNA surveillance prior to, and during, adjuvant radiotherapy.

Blood samples for ctDNA analysis should be collected every 3 months for up to two years from starting ctDNA surveillance and sent to the c-TRAK TN central laboratory for processing and analysis. DNA extracted from plasma will be analysed for the presence of ctDNA, and assayed as positive (ctDNA detected) or negative (ctDNA not detected). All positive ctDNA results within 12 months of a patient starting ctDNA surveillance will be notified to the ICR-CTSU in order for allocation to the therapeutic trial to be performed independently of the recruiting site.

If after the first 12 months of ctDNA surveillance, patients have not had a positive ctDNA result they will continue to have ctDNA surveillance every 3 months up to 2 years from starting ctDNA surveillance. All ctDNA blood samples collected in the second year of surveillance are exploratory, to confirm the optimal duration of ctDNA surveillance, and whether in subsequent studies two years of active surveillance as opposed to one year should be adopted. These samples will not be analysed in real-time. The exception to this is for patients who have missed blood samples within the first 12 months as a result of ctDNA surveillance suspension. For these patients real-time ctDNA testing, and allocation to trial treatment, may be extended beyond the original 12 months for a proportional amount of time to counteract the loss of surveillance samples for each patient.

Approximately 50% of patients entered into ctDNA surveillance will have moderate risk disease. The IDMC will monitor the proportional split of high/moderate risk patients as recruitment progresses and may recommend a cap to entry of moderate risk patients if the proportion materially exceeds 50%.

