1.2.1. Rationale for study design

Selection of patients for treatment on the basis of a positive ctDNA test

Although assays of MRD are standard in the management of haematological cancers, this will be one of the first studies to assess whether ctDNA assays have clinical utility in guiding further therapy. Patients recruited into the c-TRAK TN study will be of moderate or high risk of future relapse. The inclusion criteria, on which risk for relapse are based, are similar to many previous adjuvant therapy studies for breast cancer (for example, BEATRICE NCT00528567 [16]) that have randomised all patients unselected to treatment or placebo. However, in these studies many patients never relapse, are consequently treated unnecessarily, and do not contribute to the primary endpoint of the study. In c-TRAK TN we will use assays of ctDNA to further select from within this population a set of patients who are at very high risk of relapse (i.e. those with a positive ctDNA test).

Prior to the implementation of protocol v6.0 during the original randomised component of the trial, this high risk population was randomised between intervention with medicinal product or observation. The standard of care for these patients is observation, and no treatment will be withdrawn as a result of ctDNA testing.

In protocol version 6.0, following recommendations made by the c-TRAK TN IDMC (further detail provided in the paragraph below), the trial design changed into the non-randomised component; randomisation was removed and all patients with a positive ctDNA result will be allocated to intervention with pembrolizumab. Patients who were previously randomised to observation and are continuing with ctDNA surveillance, will be asked to re-consent and subsequently be allocated to pembrolizumab at the next positive ctDNA test.

Rationale for the change in study design – June 2020 (protocol v6.0)

Study progress to date has provided data enhancing the evidence that ctDNA presence in the blood of patients treated for moderate and high risk TNBC is a definitive positive predictor of disease recurrence. In addition to this, data from external sources and emerging data from this trial suggest that instances of overt metastatic disease in these patients presents more frequently than initially predicted at study onset, that

c-TRAK TN Protocol

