ctDNA detection is associated with near inevitability of disease recurrence in triple negative breast cancer, and that ctDNA does not spontaneously clear from the blood.

There is also new evidence for immuno-oncology therapy in TNBC; in 2019, the FDA granted accelerated approval for atezolizumab in combination with nab-paclitaxel in the treatment of patients with unresectable locally advanced or metastatic triple negative breast cancer, based on the findings from the phase III double-blind Impassion132 trial (NCT02425891) [17], further reinforcing the potential benefit of the interventional treatment arm within the study.

Taking this new data into account, the c-TRAK TN Independent Data Monitoring Committee proposed that the observation arm of the study was no longer required and should be closed. Following implementation of protocol v6.0, any patient with a subsequent ctDNA positive result detected in the blood (including those that had already been randomised to observation and remain in ctDNA surveillance) will be given the option to commence pembrolizumab treatment. This recommendation was endorsed by the ICR-CTSU Breast Systemic Therapies Trial Steering Committee and protocol version 6.0 was amended to close randomisation within the trial, with all patients allocated to treatment intervention.

Novel primary endpoint of sustained clearance of ctDNA

Even in patients with triple negative breast cancer, the most aggressive of breast cancer subtypes, the risk of relapse after treatment of primary breast cancer is relative low. The BEATRICE study [16] recently reported an invasive disease free survival relapse at 3 years occurred in only 16% of patients in the control group. Consequently phase III studies are large, and costly, with BEATRICE recruiting 2591 patients.

In the c-TRAK TN study we propose a novel primary endpoint of sustained clearance of ctDNA, defined as 'Absence of detectable ctDNA or disease recurrence 6 months (24 weeks) after commencing pembrolizumab'. This endpoint is chosen as a surrogate endpoint of treatment efficacy, which is anticipated to correlate with long-term outcome. A very similar primary endpoint (comparison of circulating tumour cell (CTC) detection rate at week 18 between trastuzumab treatment arm and observational arm) has been used in other studies in the adjuvant setting (TREAT-CTC, NCT01548677: Efficacy Study of Herceptin to Treat HER2-negative CTC Breast Cancer).

Use ctDNA diagnostics for detection of MRD

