3.2. Therapeutic Trial

Patients who have positive detection of ctDNA on or before their 12 month ctDNA surveillance assessment will be allocated to pembrolizumab treatment within the therapeutic trial centrally by ICR-CTSU.

Prior to the implementation of protocol v6.0 during the randomised component of the trial, patients who had positive detection of ctDNA on or before their 12 month ctDNA surveillance assessment were randomised centrally by ICR-CTSU in a 2:1 ratio to pembrolizumab treatment or observation (continued blinded ctDNA surveillance).

All patients randomised to observation prior to implementation of protocol v6.0 who remain in ctDNA surveillance, will transition to the non-randomised trial component following re-consent, and be allocated to pembrolizumab at the next positive ctDNA result.

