Prior to the implementation of protocol v6.0 during the randomised component of the trial, if a patient was randomised to the observation group, the treating team and patient were **not** informed that randomisation had taken place in order to remain blinded to the positive ctDNA result the patient would continue to have blood samples collected for ctDNA analysis as described in section 8.

Following implementation of protocol v6.0, all patients who were previously randomised to observation and remain in ctDNA surveillance will transition to the non-randomised component of the trial following reconsent, and be allocated to pembrolizumab at the next positive ctDNA result.

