7.2.2. Blood sample collection during ctDNA surveillance

At registration, an additional sample for ctDNA surveillance should be taken. This will be analysed and used for surveillance for patients who at the time have completed standard therapy **as defined in section 3.1.**

The baseline blood sample for ctDNA surveillance should be taken within **4 weeks** of notification from the ICR-CTSU that the patient has a trackable mutation and so can commence ctDNA surveillance, or within **4**

c-TRAK TN Protocol

weeks of completing adjuvant chemotherapy, whichever occurs later. However, for patients receiving adjuvant capecitabine, the first ctDNA surveillance sample should be taken 3 months +/- 2 weeks after the patient commenced capecitabine, or after the patient has discontinued capecitabine permanently within the first 3 months if treatment was stopped for reasons other than disease progression. Patients may start ctDNA surveillance prior to, and during, adjuvant radiotherapy.

Subsequent blood samples should be taken every 3 months (+/-2 weeks) for up to 2 years from starting ctDNA surveillance or until disease recurrence, unless the patient is allocated to the pembrolizumab treatment group (see sections 9 and 10).

During ctDNA surveillance, at each visit 40ml (4 x 10ml) blood should be collected in the ctDNA preservative tubes provided. Further details regarding the collection of blood samples for ctDNA analysis are given in the c-TRAK TN Investigator laboratory manual.

If a blood sample is of insufficient quality for analysis, ICR-CTSU will contact the treating team to request that a further blood sample is collected and sent to the c-TRAK TN central laboratory. In such a case, the patient should be invited to attend the clinic as soon as possible in order to provide another blood sample.

7.2.3. ctDNA surveillance results

ctDNA blood samples should be sent to the c-TRAK TN central laboratory for mutation analysis. The results from the ctDNA analyses performed during surveillance will not be provided to the treating team or patient.

Should a patient's blood sample be ctDNA positive within 12 months of starting surveillance, or at registration for patients that have completed standard therapy at the time of registration **as defined in section 3.1**, the c-TRAK TN central laboratory will notify ICR-CTSU and the patient will be allocated to pembrolizumab treatment within the therapeutic trial (see section 9).

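### Former observation patients are to be treated at their next positive ctDNA result up to month 24, but the testing and notification rules stop at month 12

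*Protocol*

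**What the plan says.** **The entitlement.** Section 1.2.1 says that former observation patients will be "asked to re-consent and subsequently be allocated to pembrolizumab at the next positive ctDNA test". It describes the v6.0 option of treatment as open to "any patient with a subsequent ctDNA positive result detected in the blood (including those that had already been randomised to observation" and still in surveillance). Section 3.2 says they will "be allocated to pembrolizumab at the next positive ctDNA result". Section 3.2.2 says that all patients "previously randomised to observation and remain in ctDNA surveillance will transition to the non-randomised component of the trial following reconsent". The Trial Summary, section 3 and section 17 repeat the rule. None of these places puts a month-12 limit on the qualifying positive. Under section 9, observation patients had 3-monthly sampling for up to 2 years, handled in the same way as for patients who had stayed negative.

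**The operating rules.** Section 3.1: "All positive ctDNA results within 12 months of a patient starting ctDNA surveillance will be notified to the ICR-CTSU", so that allocation can follow. Section 7.2.3 opens its rule with "Should a patient's blood sample be ctDNA positive within 12 months of starting surveillance", adds positives at registration for patients who had already finished standard therapy, and has the laboratory notify ICR-CTSU for allocation.

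**Year 2.** Section 3.1: "All ctDNA blood samples collected in the second year of surveillance are exploratory". The section adds that they are not tested in real time. It names one exception: for patients who lost first-year samples to the suspension, "real-time ctDNA testing, and allocation to trial treatment, may be extended beyond the original 12 months for a proportional amount of time".

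**The concern.** The allocation rule and the rules that put it into effect do not fit together. Allocation needs two earlier steps: the laboratory tests the sample promptly, and the result reaches ICR-CTSU. For a former observation patient past month 12 the protocol prescribes neither. Staff working from 3.1 and 7.2.3 would have no reason to test or report the sample; staff working from 3.2 would expect the patient to be treated.

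These patients were randomised because they were already ctDNA positive. Section 1.2.1 says that recurrence after ctDNA detection is close to certain in this disease and that ctDNA does not clear without treatment. It gives this as the reason for closing the observation group. Delay matters, because macroscopic disease on the staging scan rules out pembrolizumab in the trial (3.2.1, 9.3). A positive that is found only when stored samples are run later may come after that point.

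**Working it through.** The check compares the rules and counts visits. The protocol states no figure on this point to reproduce.

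**Inputs**
- Sampling at months 0, 3, 6, 9, 12, 15, 18, 21 and 24 (schedule in 8.2): 9 samples, of which 4 fall after month 12.
- Randomisation to observation could follow a positive at any sample up to and including month 12 (section 3).
- Notification covers positives within 12 months of starting surveillance (3.1, 7.2.3). The month-12 sample is counted as inside the limit.

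**Step 1: samples that could carry the next positive.** For a trigger at month t, the samples left are those with t < v ≤ 24. Those covered by the notification rule are the ones with t < v ≤ 12.

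| Trigger month | Samples left to month 24 | Covered by the 12-month rule | Not covered |
|---|---|---|---|
| 0 | 8 | 4 | 4 |
| 3 | 7 | 3 | 4 |
| 6 | 6 | 2 | 4 |
| 9 | 5 | 1 | 4 |
| 12 | 4 | 0 | 4 |

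For a month-12 trigger the next-positive rule cannot operate through the stated notification route at all, unless the suspension extension applies.

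**Step 2: does another rule fill the gap?**
- *Suspension extension (3 and 3.1).* It is permissive, proportional to the first-year samples missed, and unrelated to observation status. A patient already past month 12 when the suspension began on 19 March 2020 lost no first-year sample to it and gains nothing.
- *Sections 1.2.5 and 19.2.* Both show the intent to allocate every positive patient. Neither says that year-2 samples are tested in real time or that their results are notified, and 19.2 itself depends on a confirmed positive result.
- *Section 9.* Observation patients were sampled in the same way as never-positive patients, whose year-2 samples are not run in real time. If that practice simply continues, the observation patients' samples are not run in real time either.

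**Step 3: upper limit on the number affected.** The planned observation group is the number positive minus the number allocated pembrolizumab (table in 19.1.2):
- 24% positivity: 36 − 24 = 12
- 30% positivity: 45 − 30 = 15
- 45% positivity: 68 − 45 = 23

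Section 19.1.1 agrees with the middle case: 10% of 150 = 15. These are planned group sizes, not counts of affected patients. The patients affected are only those who are past month 12, free of recurrence, re-consented and outside the suspension extension. The protocol does not say how many patients were under observation when v6.0 took effect, so this number cannot be calculated.

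**The case against.** The strongest reply is that the protocol is silent here rather than contradictory.

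- **The notification sentences are not exclusive.** They say when notification must happen and do not forbid it later, so a laboratory could obey them and 3.2 together. This is true. But they are the only notification rules in the protocol, and permission to notify a later positive is not an instruction to test for one.
- **The year-2 restriction is aimed at never-positive patients.** The Trial Summary, the footnote to the current schema and the opening of the relevant paragraph in 3.1 all point that way, and the stated purpose of those samples (finding the best length of surveillance) fits that group better. This reading is fair, and it removes the exploratory label as a direct obstacle. It does not supply real-time testing, and the 12-month notification sentences carry no such qualifier.
- **The specific transition rule should override the general one.** Sections 3, 3.2 and 17 set the two side by side, and ICR-CTSU knows who was randomised to observation. This settles what was intended. It governs allocation once a positive is known, not how the positive comes to be known.
- **The 12-month limit in 7.2.3 could be deliberate.** The section was partly updated for v6.0, since it now speaks of allocation to pembrolizumab. Yet it still withholds surveillance results from the treating team and patient, whereas 1.2.5 says that all results are now open. That suggests an incomplete update.
- **The impact is speculative.** It may be that no patient meets all the conditions. This stands, and it limits the weight of the point.

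**Conclusion.** The concern holds. Protocol v6.0 clearly intends to treat re-consented observation patients at their next positive result for as long as they remain in surveillance, but it states no testing and notification route after month 12. In every case four later samples fall outside the notification rule, and for a month-12 trigger those are all the samples that remain.

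This rests on two assumptions: that sections 3.1 and 7.2.3 are what the laboratory works from, since any separate laboratory instruction is not in the protocol, and that the suspension extension does not happen to cover the patient. The number affected is unknown, probably small and possibly zero. The consequence is missed or late access to treatment for individual patients; no effect on the primary analysis is claimed. It should be fixed because the possible harm to a patient is serious and the correction is small.

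**What to change.** - **Section 3.1:** add re-consented former observation patients to the exception that allows real-time testing after month 12, and state that their positives are notified to ICR-CTSU at any scheduled sample up to month 24.
- **Section 7.2.3:** lift the 12-month condition for the same patients, so that a later positive leads to notification and to allocation under 3.2.
- **Laboratory:** issue a matching instruction, with ICR-CTSU identifying the patients concerned.

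The cost is one sentence in each section, the instruction, and running at most four second-year samples per patient on receipt instead of in batches. The blood is already being collected. Limiting the next-positive rule to the first 12 months would also remove the mismatch, but it would withdraw the option that v6.0 was written to give.
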